10.3.2 Subject Instructions

- All subjects must be given Subject Instructions (see APPENDIX D) for use of the study lenses. Subjects must comply with the instructions provided to them.
 Subject Instructions will be supplied to the Investigator by Bausch + Lomb for distribution to the subject.
- b. All subjects must refer to the Bausch + Lomb Biotrue Multi-Purpose solution package insert for care instructions, precautions, and warnings related to contact lens wear.
- c. The Investigator or other designee must review instructions and warnings for lens wear, lens care, handling, cleaning, and disinfecting with the subject.
- d. Any subject who does not follow instructions to a degree that, in the Sponsor's or Investigator's opinion, jeopardizes the subject's well-being or the validity of the study, must be discontinued.

10.3.3 Fitting Guide

The Investigator should refer to the Fitting Guide (see APPENDIX E) for fitting the test and control lenses.

10.4 Other Materials

10.4.1 Care System

All subjects will be dispensed the following care products for use during the study:

- Biotrue Multi-Purpose solution for daily rinsing, cleaning, disinfecting, and storing their lenses in lens cases. All commercially available Biotrue bottles include a green lens case.
- ReNu MultiPlus Lubricating and Rewetting Drops for use as needed during the study

Investigators will be provided Biotrue Multi-Purpose solution and lens cases for return of study lenses to the Sponsor at the end of the study.

NOTE: Use of other contact lens care products is not allowed during the study.

10.5 Packaging and Labeling

The test lenses (custom samifilcon B) used in this study will be packaged in glass vials with investigational labels. The labels will contain the following information:

- Lens power
- Base curve
- Lens diameter
- Lot number
- Expiration date
- Manufacturer's name and location
- Caution statement

The control lenses (Alden Optical HP Sphere) used in this study will be provided in the glass vials. The labels will contain the following information:

- Lens power
- Base curve
- Lens diameter
- Lot number
- Expiration date
- Manufacturer's name and location

10.6 Accountability

The unmasked designee will be responsible for keeping current and accurate records of the amount of study test lenses received and dispensed, and its disposition. The study lenses must be stored under the appropriate conditions in a secure area and are to be dispensed only to subjects enrolled in the study, in accordance with the conditions specified in this protocol. During the course of the study, the unmasked designee must maintain an inventory of all lenses dispensed to or returned by the subject, including subject identifiers. A Product Accountability Log will be provided to the sites to maintain records of the study lenses assigned to each enrolled subject.

At time points throughout the study and/or upon completion of the study, the Sponsor/Sponsor's representative will review and verify the Investigator's Product Accountability Logs. Following verification, and as directed by the Sponsor, all worn and unworn lenses must be returned to the Clinical Trial Materials Supply Management at the address listed on the Personnel and Facilities page.

10.7 Masking/Unmasking

This study is double-masked; therefore, the Investigator/site staff, subjects, and Bausch + Lomb personnel or designee(s) involved in the collection of study data will be masked to the study lenses. Each site must have an unmasked designee that will be responsible for dispensing and accountability. This designee shall not participate in study assessments that may cause bias to the study data. Study Monitors will become unmasked during site visits when they perform product accountability.

Lens markings on both products are not product-specific. Markings and lens tints are similar between products and are indistinguishable.

Randomization will be produced prior to study enrollment by an unmasked statistician not otherwise involved in the trial. An unmasked designee will be responsible for dispensing the test and control lenses according to the randomization system. Investigators will not have access to the randomization system information and lenses will be dispensed directly to the subject, thereby maintaining Investigator masking. In an effort to ensure that both the Investigator and subject remain masked, the unmasked designee MUST dispense the study lenses and MUST remove lenses from their glass vials out of the Investigator's and subject's sight immediately prior to dispensing. Subjects will not be given additional replacement lenses to take home, thereby

maintaining subject masking. A reserve pair will remain at the site if a replacement is needed.

The Investigator should contact the Medical Monitor prior to unmasking of study lenses. In an emergency situation, however, where knowledge of the study lenses is critical to subject safety, the code may be broken by requesting the allocated treatment for that subject from the unmasked designee.

The Investigator must notify the Sponsor as soon as possible after unmasking. In addition, the Investigator must record the date, time, and reason for unmasking the study treatment in the source documentation.

10.8 Replacement Lenses

Replacements are permitted for damage, satisfaction, and vision at the discretion of the Principal Investigator. All lens replacements need to be tracked for reason and date and must also be rechecked for fit.

A reserve pair of study lenses for each dispensed subject should be retained in-office at all times in case a non-scheduled lens replacement is required. If the reserve is used, an immediate replacement order is required. Any additional/replacement of test or control products (in the case of loss or damage) must be ordered through Clinical Trial Materials using the Replacement Lens Order Form for Study #886. Do not order through Bausch + Lomb Customer Service. The form can be scanned to

10.9 Risk Assessment

The assessments required for the study are routinely performed and are standard of care for contact lens wearers. The subjects will be informed of any potential study-specific risks in the ICF or if new risks become apparent during the study.

10.10 Methods of Assigning Subjects to Treatment Groups

10.10.1 Treatment Allocation

Randomized treatment assignments will be allocated to eligible subjects sequentially using the next available assignment in the randomization schedule.

10.10.2 Randomization Method

Randomization will be provided to the sites via the randomization system. When it is time to randomize an eligible subject, the unmasked designee will use the randomization system to obtain the subject's treatment assignment.

11.0 EFFECTIVENESS AND SAFETY VARIABLES

11.1 Primary Effectiveness Variable

The primary effectiveness endpoint will be statistical non-inferiority with respect to mean distance high-contrast logMAR lens VA for each eye between the test and control lenses.

11.2 Secondary Effectiveness Variables

Not applicable.

11.3 Safety Variables

The primary safety endpoint will be statistical non-inferiority with respect to the proportion of eyes with any slit lamp findings Grade >2 at any follow-up visit between the test and control lenses.

12.0 STUDY METHODS

12.1 Study Visits

Refer to APPENDIX A for a schedule of visits and parameters and APPENDIX B for methods of clinical evaluation.

Following identification of a potential subject, the Investigator (or designee) will explain the purpose of the study, procedures, risks/benefits, and subject responsibilities to the potential subject. The subject's willingness and ability to meet the follow-up requirements of the study will be determined. If the subject chooses to participate in the investigation, written informed consent will be obtained. The subject and the person obtaining written consent will sign and date the IRB-approved ICF. Both the Investigator and subject must keep the signed ICF document. It is strongly preferred that the signed original document be retained in the subject's records, while a copy be provided to the subject. In addition, the applicable privacy regulation requirements must be met.

12.1.1 Screening Visit (Visit 1)

NOTE: All VA measurements MUST be made using a phoropter.

A Screening Log will be provided by the Sponsor to track all consented subjects that the Investigator interviews regarding the study. Once all available lines on the Screening Log have been completed, or the Investigator has fulfilled his/her quota of subjects, the Investigator will sign and date the form to verify that all the subjects who interviewed for the study have provided informed consent and Health Insurance Portability Accountability Act (HIPAA) authorization and any other applicable state requirements. The Investigator will send a copy of the Screening Log to the Sponsor. The Investigator will retain the original document for his/her records.

After obtaining written informed consent, prospective subjects will be screened to determine whether they meet the entry criteria for the study.

Screening will proceed as follows:

- a. Enter the subject information on the next available line of the Screening Log.
- b. Collect subject's medical history
- c. Collect the following lens history information from the subject:
 - Average number of days per week worn
 - Average daily wearing time, hours per day
 - Average hours of comfortable wear per day

- Hours lenses worn on the day of this visit
- Current lens brand and lens wear modality
- Current lens care products
- d. Collect demographic and baseline information and perform the following baseline assessments (without lenses) and record in the subject's source document:
 - Spherocylindrical refraction
 - Distance best spectacle-corrected visual acuity (BSCVA)
 - Keratometry
- e. Perform a slit lamp examination (remove the lenses if the subject wore lenses to the visit). Record and diagram the results and findings in the subject's source document and appropriate eCRF:
 - Any ungraded finding marked as "Present"
 - Any corneal scars
 - Any neovascularization within the central 6 mm of the cornea
 - Any corneal staining
 - Any corneal infiltrate (record details on the Corneal Infiltrates Evaluation Form [APPENDIX C])
 - any other graded slit lamp findings Grade 2 or greater
- f. Indicate on the Screening Log whether the subject is a "Screen Pass" or "Screen Fail."
 - "Screen Fail" subjects are ineligible and cannot be randomized in the study. The reason for screen failure must be documented on the Screening Log and in the subject record and must be maintained with a copy of their ICF.
 - Only "Screen Pass" subjects should be randomized in the study.
- g. If the subject is eligible, collect Symptoms/Complaints and Subjective Assessment information from the subject regarding their habitual lenses.
- h. Assign subject numbers based on the randomization system. The unmasked designee will determine the subject's randomized lens by using the randomization system and record on the Screening Log.
- i. Assess BSCVA to determine subject prescription. The prescription determined from this fitting assessment will be used to dispense/order test or control lenses according to the lens to which the subject is randomized.
- j. Record the lens parameters to be dispensed/ordered based on the diagnostic fitting.
- k. For each subject, use the lens order form to order the appropriate study contact lenses (test or control). Schedule the subject for their Dispensing Visit within 30 days.

- 1. Collect/assess all AEs, including serious or significant non-serious AEs, since consent was signed.
- m. For female subjects, re-emphasize the exclusion criterion stating that if the subject is of childbearing potential and is pregnant and or breast feeding, she is ineligible to be a part of the study.

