9.2 Selection of Study Population

Written informed consent, enrollment in the study, or dispensing of study products cannot begin until the Investigator has received Institutional Review Board (IRB) approval to conduct the study. The Sponsor and IRB must approve any advertising used to recruit subjects prior to use of that advertising.

All consented subjects must be accounted for, whether they participate in the study or not. Bausch + Lomb will provide a Screening Log on which to enter information for each

subject who signs an Informed Consent Form (ICF). All screened subjects must be entered onto the Screening Log, in the order in which they were consented, where they will be assigned a sequential subject identification (ID) number. Once a potential subject is consented and their initials are entered onto the Screening Log, the Investigator should proceed with Screening procedures.

Potential subjects are deemed either "Screen Pass" or "Screen Fail." "Screen Fail" subjects are subjects who have not met the study inclusion criteria or have met the exclusion criteria and cannot be randomized into the study.

"Screen Pass" subjects have met all of the study inclusion criteria and have not met any of the exclusion criteria. Only "Screen Pass" subjects can be randomized to receive the study lenses and can be assigned a subject identification (ID) number from the randomization system.

Once a subject is randomized, a subject is considered active and must be accounted for at every visit until exited (completed or discontinued) from the study, even if they are not dispensed study materials. Refer to Section 9.2.4 for subjects determined to be lost to follow-up.

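### As worded, screening step h puts the randomized lens on a log that the Investigator signs and keeps, contrary to the masking rule in section 10.7

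*Combined protocol and SAP*

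**What the plan says.** Section 12.1.1, step h, first has subject numbers assigned from the randomization system. It then has the unmasked designee find the subject's "randomized lens by using the randomization system and record on the Screening Log".

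The Screening Log is one running form for the site. Section 9.2: "All screened subjects must be entered onto the Screening Log, in the order in which they were consented". Section 12.1.1 uses it again for every new subject, at step a ("Enter the subject information on the next available line of the Screening Log") and at step f, where screen pass or fail is marked on it.

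The Investigator takes custody of it. Section 12.1.1 sets the moment of signature: "Once all available lines on the Screening Log have been completed, or the Investigator has fulfilled his/her quota of subjects". The signature serves to confirm consent and privacy authorization; in the protocol's words, "the Investigator will sign and date the form to verify". A copy goes to the Sponsor, and "The Investigator will retain the original document for his/her records".

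Section 10.7 states that the Investigator, the site staff, the subjects and the Sponsor personnel who collect data are masked as to the study lens. Investigators are kept out of the randomization system's information. An unmasked designee dispenses the lenses out of sight and takes no part in assessments that could be biased. In an emergency the allocation is obtained by asking that designee.

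**The concern.** The protocol goes to some length to keep the lens type from the Investigator, yet step h appears to write it on a form that the Investigator signs and files. A site that follows step h in its plain sense cannot also follow section 10.7.

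Both primary endpoints are at stake: distance high-contrast lens VA and slit lamp grade. Both are measured at site visits by staff who are supposed not to know the lens, and both depend in part on how the examiner tests, prompts or grades. Masking that has been lost cannot be restored for that subject.

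**Working it through.** No formula applies, and the plan gives no figure to reproduce. The check sets the provisions side by side.

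1. **What is entered.** In step h the verb *record* has no object of its own. The nearest candidate is the randomized lens, which the designee has just determined in the same sentence. The other candidate is the subject number, from the preceding sentence of step h. The lens is the more natural reading; the number is possible.

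2. **Who has the document.** The Investigator signs it and keeps the original (12.1.1). No section describes a concealed column, a coded entry or a separate unmasked version.

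3. **Which rule it meets.** The rule that applies is the general one in 10.7, that the Investigator and site staff are masked as to the study lens. The bar on access in 10.7 concerns information in the randomization system. It does not by its terms reach an entry on a paper log, so it is supporting evidence only.

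4. **Whether exposure must wait for the signature.** It need not. The log gains a line and a pass/fail mark for each new subject, while earlier subjects' entries stand on it. Section 9.2 adds that once "their initials are entered onto the Screening Log, the Investigator should proceed with Screening procedures". Steps a and f name no actor, and Appendix A allows tasks to be delegated, so early sight of the entries is possible but not certain.

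5. **Timing against the endpoints.** Randomization is at Screening, Day -30 to Day -7 (Table 1, Appendix A). Study lenses are first worn and tested on Day 1. The interval is 7 days from Day -7 (8 if a Day 0 is counted) and 30 days from Day -30 (31 with a Day 0). The entry therefore stands for at least 7 days before that subject's first study-lens assessment. If the quota is met when the last subject is randomized and the log is signed promptly, the Investigator holds that subject's entry before the Dispensing Visit. Earlier subjects may then be part-way through follow-up. The signing date is not fixed and could fall later.

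6. **What can be counted.** Planned eyes: 84 × 2 = 168. Lens VA is read at 5 visits: 168 × 5 = 840. Follow-up slit lamp grading is scheduled at 4 visits: 168 × 4 = 672. With no losses, these are simply all the scheduled primary-endpoint assessments, since all follow randomization. They are a ceiling and say nothing about how many would be made by someone who had seen the allocation. That number runs from none to all.

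7. **Neighbouring steps.** Step k orders test or control lenses and step j records the lens parameters; neither names an actor. The base curve is 8.6 mm for the test lens and 8.3 mm for the control (10.1, 10.2), so a recorded base curve would identify the arm.

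**The case against.** The best defence is that step h means a number. Section 9.2 has sequential IDs assigned on the Screening Log and says that subjects who pass screening receive an ID from the randomization system. Step h itself opens with subject numbers. The emergency route in 10.7, which goes through the designee, suggests that the authors did not expect the log to show the lens. The form is supplied by the Sponsor and is not in the documents, and its columns might settle the matter. The signature is there to verify consent and privacy authorization, not allocation. Section 10.6 already gives the designee the lens inventory.

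Much of this stands. It shows that the two sections can be read together and that exposure is not established. It does not rescue the wording: the number-only reading has to be supplied by the reader, and a site following the plainer sense would write down the lens. The emergency route also cuts the other way, because it would be needless if the lens stood on a log that the Investigator holds.

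A reader might infer more than the documents support:

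- **That Investigators will be unmasked.** This depends on the form, on who completes it and on when it is signed, none of which is known.
- **That the copy sent to the Sponsor is itself a breach.** The recipient's masking status is not stated.
- **That entries in sequence let sites predict later assignments.** Randomization is stratified by site, but no block size is given.
- **That all 840 VA readings and 672 gradings are compromised.** Those counts would be the same for any remark about masking.

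**Conclusion.** The point holds as a conflict of wording between 12.1.1 step h and 10.7. On the natural reading, the allocation is written on a document available to the Investigator, who must be masked. It is not a fault in the double-masked design, and it does not show that masking would fail in practice. The conclusion rests on two assumptions: that *record* takes the lens as its object, and that the form does not conceal the entry. If only a number is entered, there is no breach, but step h still needs to say so.

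The size and direction of any bias cannot be computed from the documents. Confidence is moderate. The text is wrong as written and should be fixed; an exposure that may be zero does not justify a higher rating.

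**What to change.** - **Step h.** State that the Screening Log carries only the subject or randomization number and the fact of randomization, and never the assigned lens or anything that reveals it. The other entries (initials, pass or fail, reason for failure) stay.
- **Section 10.6.** Have the unmasked designee record the assigned lens in the accountability records already kept there. Add that the designee holds these records and that masked staff may not see them. The clause is needed because 10.6 also describes the Product Accountability Logs as the Investigator's.
- **Steps j and k.** For consistency, name the unmasked designee as the person who completes the test/control order form and records any parameter that identifies the arm. Keep those records from masked staff too. The order form must identify the lens, so the aim is restricted access rather than a single record.

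The cost is a few sentences and, if the form has a lens column, a revised Screening Log. Each site already has the designee and the accountability log. Monitors already become unmasked when they check accountability (10.7), so the move exposes no further role. Sample size, endpoints and analysis do not change.

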12.1.2 Dispensing Visit (Visit 2)

- a. Collect/assess all AEs, including serious or significant non-serious AEs.
- b. Perform a slit lamp examination (remove the lenses if the subject wore lenses to the visit). Record all slit lamp findings and, at a minimum, sketch the following in the subject's source document:
 - any ungraded finding marked as "PRESENT"
 - any new corneal scars
 - any neovascularization within the central 6 mm of the cornea
 - any corneal staining
 - any corneal infiltrate (record details on the Corneal Infiltrates Evaluation Form [APPENDIX C])
 - any other graded slit lamp findings Grade 2 or greater
- c. Dispense study lens, record sphere power, record in Product Accountability Log. In an effort to ensure that both the Investigator and subject remain masked, the unmasked designee MUST dispense the study lenses and MUST remove lenses from their glass vials out of the Investigator's and subject's sight immediately prior to dispensing.
- d. Subject inserts pair of the study lenses in his/her eyes.

NOTE: Study lenses should be allowed to equilibrate a minimum of 3 minutes on the eye.

- e. After a minimum of 3 minutes, perform the following assessments:
 - Collect Symptoms/Complaints and Subjective Assessment information
 - Distance high-contrast logMAR lens VA
 - Over-refraction and distance VA
 - Lens wettability, centration, movement
 - Lens deposits

For each eye, compare the distance high-contrast logMAR lens VA to the distance BSCVA obtained at the Screening visit. If the VA has decreased by ≥5 letters (0.1 logMAR), explain.

- f. Dispense lens case. Instruct the subject to store their study lenses in the lens case filled with Bausch + Lomb Biotrue MPS according to the Subject Instructions (APPENDIX D).
- g. If the subject is discontinued or exited at this visit, complete the Exit Visit eCRF.

- h. For female subjects, re-emphasize the exclusion criterion stating that if the subject is of childbearing potential and is pregnant and or breast feeding, she is ineligible to be a part of the study.
- 12.1.3 1-Week, 1-Month, 2-Month, and 3-Month Visits (Visits 3, 4, 5, and 6)
- NOTE: All VA measurements MUST be made using a phoropter.
- NOTE: If all scheduled visits are performed on time and the subject completed the 3-Month Visit, the Exit Visit will be done at the same time.
- NOTE: Study lenses should not be dispensed at this visit unless replacement lenses are required. Lenses worn to this visit should be returned to the subject for use until the next scheduled visit.
- NOTE: If the subject does not come to a visit wearing lenses due to requiring a replacement and is not experiencing any problems, it is preferred to do an Unscheduled Visit for Product Dispensing Only and reschedule the current visit within the visit window. Refer to Unscheduled Visit, Section 12.1.4.
 - a. Collect/assess all AEs, including serious or significant non-serious AEs.
 - b. Collect the following lens information from the subject:
 - Average number of days per week worn
 - Average daily wearing time, hours per day
 - Average hours of comfortable wear per day
 - Hours lenses worn on the day of this visit
 - c. Collect Symptoms/Complaints and Subjective Assessment information from the subject regarding their study lenses.
 - d. Evaluate the lenses (while on eye), and record the following assessments:
 - Distance high-contrast logMAR lens VA
 - Over-refraction and distance VA
 - Lens wettability, centration, movement
 - Lens deposits

For each eye, compare:

- The distance high-contrast logMAR lens VA at this visit to the distance high-contrast logMAR lens VA obtained at the Dispensing Visit.
- The distance high-contrast logMAR lens VA at this visit to the distance BSCVA obtained at the Screening Visit
- If the VA has decreased by ≥ 10 letters (0.2 logMAR), explain.
- e. Perform a slit lamp examination (remove the lenses if the subject wore lenses to the visit) and note the following:
 - Any ungraded finding marked as "Present"
 - Any new corneal scars
 - Any neovascularization within the central 6 mm of the cornea
 - Any corneal staining

- Any corneal infiltrate (record details on the Corneal Infiltrates Evaluation Form – APPENDIX C)
- Any other graded slit lamp findings Grade >2
- f. For female subjects, re-emphasize the exclusion criterion stating that if the subject is of childbearing potential and is pregnant and or breast feeding, she is ineligible to be a part of the study.

